#### **4.4 EXPLORATORY ESTIMANDS AND ANALYSIS**

This section defines estimands for exploratory efficacy endpoints listed in [Table 2](#).

##### **4.4.1 Estimands for Time-to-Event Endpoints**

**Estimand:** The estimand is the difference in endpoint, as expressed by the HR, between the higher and approved dose of ocrelizumab arms in patients with RMS and regardless of adherence to the randomized treatment or use of an approved MS DMT medication.

##### **Endpoints:**

- Time to onset of 24-week confirmed  $\geq 20\%$  increase in T25FWT (CIT25FWT24)
- Time to onset of 24-Week confirmed disability progression in EDSS (CDP24)
- Time to onset of 12-week confirmed  $\geq 20\%$  Increase in 9-HPT (CI9-HPT12)
- Time to onset of 24-week confirmed  $\geq 20\%$  Increase in 9-HPT (CI9-HPT24)
- Time to onset of 12-week confirmed  $\geq 8$ -point worsening in SDMT
- Time to onset of cCDP12 or 12-week confirmed  $\geq 4$ -point worsening in SDMT
- Time to onset of cCDP12 or 12-week confirmed  $\geq 8$ -point worsening in SDMT
- Time to onset of cCDP12 individual components independent of protocol-defined relapses
- Time to onset of cCDP24 and cCDP24 individual components independent of protocol-defined relapses
- Time to onset of 12-week confirmed protocol-defined relapse associated worsening in cCDP12 and individual components

Time to onset of protocol-defined relapse associated worsening in the individual components of cCDP12 is defined similarly to time to onset of the individual components of cCDP12, except that one additional condition must be satisfied:

- Progression must occur within 90 days of a protocol defined relapse.

If progression occurs and it does not satisfy the above condition, then 1) the progression is not considered a protocol-defined relapse associated worsening event, 2) time to

onset of protocol-defined relapse associated worsening is censored at the time of the progression.

Time to onset of protocol-defined relapse associated worsening in cCDP12 is defined as the time to onset of the first occurrence of protocol-defined relapse associated worsening in the individual components of cCDP12.

**Summary Measure and Primary Estimator:** The HR will be the summary measure and the Cox proportional hazards model will be the primary estimator. The estimation method will be the same as for the primary estimand (Section 4.2.2).

In order to estimate the aforementioned estimand, the same **intercurrent event** handling strategies as those for the primary endpoint in Section 4.2.2 will be applied.

Missing data resulting from patients that withdraw their consent to participate in the study and/or a serious GCP breach will not be imputed (including following death).

#### **4.4.2 Estimands for Continuous Endpoints at Scheduled Visits**

**Estimand:** The estimand is the mean difference in the endpoint between the higher and approved dose of ocrelizumab arms in patients with RMS and regardless of adherence to the randomized treatment or use of an approved MS DMT medication.

##### **Endpoints:**

- Change from baseline in EDSS score at Week 48 and 120
- Change from baseline in Multiple Sclerosis Impact Scale-29 (MSIS-29) physical scale at Week 48 and 120
- Change from baseline in MSIS-29 psychological scale at Week 48 and 120
- Change from baseline in Quality of Life in Neurological Disorders (Neuro-QOL) Upper Extremity Function Form at Week 48 and 120
- Change from baseline in Modified Fatigue Impact Scale at Week 48 and 120

**Summary Measure and Primary Estimator:** MMRM will be used to quantify mean difference in the endpoints between the higher and approved dose of ocrelizumab arms. The fixed effects in the model will include independent variables of randomized treatment, visit (nominal post-baseline visits as per the Schedule of Assessments), baseline outcome, treatment-by-visit interaction, baseline outcome by visit interaction, along with the randomization stratification factors. An unstructured variance-covariance structure will be applied to model the within-patient errors. The restricted maximum likelihood (REML) method will be used for estimation of variance components. The statistical significance of the estimated mean difference will be calculated by using the Wald test.

In order to estimate the estimand of interest, the following **intercurrent event** handling strategies will be applied:

**Early discontinuation from study treatment:** All data available will be included in the analysis following the treatment-policy strategy.

**Initiation of an approved MS DMT medication:** All data available will be included in the analysis following the treatment-policy strategy.

**Pregnancy:** All data pre and post pregnancy onset will be included in the analysis.

**Death:** This is anticipated to be very rare, but in case of occurrence, it will be handled with the composite strategy. That is, data after death will be treated as the worst possible score.

Only data up until Week 120 (inclusive) will be used in the analysis.

Missing data resulting from patients that withdraw their consent to participate in the study and/or a serious GCP will not be imputed (including following death).

For MSIS-29, if there are missing individual items and the respondents have a minimum of 10 completed items in the physical scale, or a minimum of 5 completed items in the psychological scale, the following imputation process will be applied to handle the missing individual items. Missing scores in the specific scale are imputed as the average of the scores of all (completed) items in that scale. For example, if a patient has completed 15 items (item 1-15) in the physical scale and the values for item 16-20 are missing, then first sum the completed items 1-15 and then divide by 15 to get their respondent-specific mean score. Then use this value as the score for each of the missing 5 items 16-20. Generate a total score as usual by summing the values of the 15 completed items 1-15 and the 5 imputed items 16-20 based on the score calculation for physical scale (above).

#### **4.4.3 Estimands for Rate of Change of Continuous Endpoints**

**Estimand:** The estimand is the mean difference in the endpoint between the higher and approved dose of ocrelizumab arms in patients with RMS where no treatment discontinuation nor initiation of alternative MS treatment can occur.

##### **Endpoints:**

- Annual rate of percentage change in thalamic volume
- Annual rate of change from baseline in total radius of T1-hypo-intense lesions (black holes)
- Annual rate of percentage change in volume of spinal cord (upper part of the spine)

The same population definition, intercurrent events handling strategies and estimator will apply as for the annual rate of percent change from baseline in total brain volume (Section 4.3.2).

For annual rate of change from baseline in total radius of T1-hypo-intense lesions (black holes),  $Y_{ij}$  represents change in the cube root of total volume of T1-hypo-intense lesions from baseline at visit  $j$  for patient  $i$ .

Missing data resulting from patients that withdraw their consent to participate in the study and/or a serious GCP breach will not be imputed (including following death).

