#### 4.3.2 Estimand for Annual Rate of Percent Change from Baseline in Total Brain Volume

**Estimand:** The estimand is the mean difference in annual rate of percent change from baseline in total brain volume between the higher and approved dose of ocrelizumab arms in patients with RMS where no treatment discontinuation nor initiation of alternative MS treatment can occur, according to the following attributes:

**Estimator:** A random coefficient regression model (RCRM) will be used to quantify mean difference in annual rate of percent change from baseline in total brain volume between the higher and approved dose of ocrelizumab arms. The mean structure of the model is as follows:

$$E[Y_{ij}|time_{ij}, T_i, X_i] = time_{ij}(\beta_0 + \alpha X_i + \beta_1 T_i + u_i),$$

where  $Y_{ij}$  represents percentage change in total brain volume from baseline at visit  $j$  for patient  $i$ ,  $time_{ij}$  is the time from baseline in years at visit  $j$  for patient  $i$ ,  $T_i$  is an indicator such that  $T_i = 1$  if patient  $i$  was randomized to the higher dose of ocrelizumab arm and  $T_i = 0$  otherwise,  $X_i$  is a vector containing the cube root of the baseline total brain volume and randomization stratification factors for patient  $i$ ,  $\alpha$  is a vector of regression coefficients for  $X_i$ ,  $\beta_0$  is the adjusted mean of the annualized rate of percentage change in total brain volume for the approved dose of ocrelizumab arm,  $\beta_1$  is the adjusted mean difference in the annualized rate of percentage change in total brain volume between the higher and approved dose of ocrelizumab arms, and  $u_i$  is a subject-specific random effect that follows a mean zero normal distribution. The statistical significance of the estimated mean difference will be calculated by using the Wald test, where the standard error is estimated using the robust sandwich variance estimator.

In order to estimate the aforementioned estimand, the following **intercurrent event** handling strategies will be applied:

**Early discontinuation from study treatment:** All data after treatment discontinuation will be treated as missing following the hypothetical strategy.

**Initiation of an approved MS DMT medication:** All data after treatment discontinuation will be treated as missing following the hypothetical strategy.

**Pregnancy:** All data pre and post pregnancy onset will be included in the analysis following treatment-policy strategy.

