**Death:** This is anticipated to be very rare, but in case of occurrence, it will be handled with the hypothetical strategy. That is, data after death will be treated as missing.

Missing data resulting from patients that withdraw their consent to participate in the study and/or a serious GCP breach will not be imputed.

Sample Statistical Analysis System code can be found below (Statistical Analysis System code is regarded as “draft” until fully validated at the analysis stage):

```
PROC MIXED DATA=dataset empirical;  
CLASS USUBJID ARMCD StratificationFactors;  
MODEL AVAL_N = ARMCD Baseline StratificationFactors / solution cl;  
RANDOM intercept / subject=USUBJID type=un;  
run;
```

where AVAL\_N is the percentage change in brain volume divided by time at each scheduled visit, and Baseline is the cube root of total brain volume at baseline.

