##### **Endpoints:**

- Proportion of patients with no change in overall severity, improvement or worsening measured with patient global impression of severity at Week 48 and 120
- Proportion of patients with no change in overall MS symptoms, improvement or worsening measured with patient global impression of change at Week 48 and 120
- Proportion of patients with no change in upper limb function, improvement or worsening measured with patient global impression of change of upper limb function at Week 48 and 120

**Summary Measure and Primary Estimator:** Ordered logistic regression will be applied to the various responder definitions at each scheduled visit between the higher and approved dose of ocrelizumab arms. The fixed effects in the model will include independent variables of randomized treatment, baseline endpoint value, and the randomization stratification factors. The statistical significance of the estimated odds ratio will be calculated with the Wald test.

In order to estimate the estimand of interest, the same **intercurrent event** handling strategies as for primary estimand in Section 4.2.2 will be applied.

Only data up until Week 120 (inclusive) will be used in the analysis.

Missing data resulting from patients that withdraw their consent to participate in the study and/or a serious GCP breach will not be imputed (including following death).

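### SAP 4.4.3 carries the brain-volume estimator over to three other MRI structures without naming a baseline covariate for them; read literally, it adjusts for whole-brain volume instead of the endpoint's own baseline, at a possible cost in precision

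*SAP*

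**What the plan says.** SAP 4.3.2 defines a random-coefficient model for the annual rate of percent change in total brain volume. Its covariate vector X_i "is a vector containing the cube root of the baseline total brain volume and randomization stratification factors for patient". The note under the sample code repeats the choice: "Baseline is the cube root of total brain volume at baseline".

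SAP 4.4.3 covers three exploratory endpoints: annual rates of change in thalamic volume, in the total radius of T1-hypo-intense lesions (black holes), and in upper spinal cord volume. It defines no model of its own and states that the same "intercurrent events handling strategies and estimator will apply as for the annual rate of percent change from baseline in total brain volume". It then makes one substitution, for black holes only: Y_ij "represents change in the cube root of total volume of T1-hypo-intense lesions from baseline at visit". It does not redefine X_i for any of the three endpoints, nor Y_ij for thalamus or cord.

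Other models in the SAP that adjust for a baseline value name the endpoint's own. The repeated-measures models in 4.4.2 include "baseline outcome, treatment-by-visit interaction, baseline outcome by visit interaction, along with the randomization stratification factors". The ordinal models in 4.4.4 include "randomized treatment, baseline endpoint value, and the randomization stratification factors". The NfL model in 4.3.3 uses baseline NfL on the log scale.

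**The concern.** In 4.3.2 whole-brain volume is the right baseline because it is the baseline of the outcome analysed. Carried over to another structure, it no longer is. A programmer who follows 4.4.3 to the letter would fit the black-hole model with whole-brain volume as its only MRI covariate, and baseline lesion volume would not appear. A programmer who reads the cross-reference in spirit would use the structure's own baseline. Both could claim to have followed the plan.

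What is at stake is the width of the confidence intervals for the dose effect on these three rates. If a structure's own baseline predicts its later change and whole-brain volume does not, the literal model leaves explainable between-patient variation in the error term.

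**Working it through.** **1. What carries over and what is replaced**

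| Element | 4.3.2 (brain volume) | Black holes (4.4.3) | Thalamus, cord (4.4.3) |
|---|---|---|---|
| Outcome Y_ij | percent change in total brain volume | replaced | not replaced |
| Covariate X_i | baseline brain volume (cube root) and stratification factors | not replaced | not replaced |

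For thalamus and cord, Y_ij has to be substituted or the model would analyse brain volume. Some endpoint-specific reading is therefore intended there. For black holes the authors wrote the substitution themselves and left X_i alone, so the literal reading is strongest for that endpoint.

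**2. Are own baselines available?** Yes. Protocol 4.5.7 makes the screening MRI the baseline scan and images the upper spine where technically possible. Each endpoint is a change from that scan, so the baseline exists wherever the endpoint can be computed.

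**3. Is there a planned figure to reproduce?** Not for these endpoints: the documents give no SD, effect size, power or correlation. The SAP's only power figure is for the primary endpoint (205 events, hazard ratio 0.66, 2:1, two-sided 5%). It reproduces as 205 events with 80.1% power, and it has no bearing on this point. Everything below rests on stated assumptions.

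**4. Black holes.** The outcome is a difference of cube roots, (V + g)^(1/3) − V^(1/3). For the same growth g = 100 mm³ (assumed):

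- V = 0: 4.64
- V = 1000 mm³: 0.323
- V = 5000 mm³: 0.113

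If growth in volume is similar across patients, baseline volume therefore drives Y strongly. Whether growth behaves that way is not documented. A simplified simulation used one change per patient and 577:288 patients (865 split 2:1). It assumed a lognormal baseline with median 1500 mm³ and log-SD 1.0 to 1.4, 5 to 25% of patients lesion-free, and uninformative brain volume. The table gives the variance of the treatment coefficient with own baseline relative to brain volume:

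| Assumed growth | Relative variance | Cut |
|---|---|---|
| 100 mm³ + 2%, constant; residual SD 0 to 1 | 0.42–0.84 | 16–58% |
| Same mean, growth CV 2 | 0.76–0.97 | 3–24% |
| 20% of lesion-free patients gain 100 mm³, the rest stay lesion-free; others CV 2 | 0.93–1.01 | none to 7% |
| Radius growth independent of baseline | 0.99–1.00 | none to 1% |

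A second set of runs, with growth CV 0.5 to 1.5, gave cuts of 18–73% with 5–25% lesion-free patients and 2–21% with none. The top of the range is thus not a bound. The result follows the assumed growth law and the lesion-free share.

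**5. Thalamus and cord.** Adjusting for a covariate that has correlation r with the patient's rate multiplies the variance by 1 − r². The SE under brain-volume adjustment relative to own baseline is √[(1 − r_brain²)/(1 − r_own²)]. With r_brain = 0:

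| r_own (assumed) | Extra SE | Power with own baseline, if 80.0% with brain volume |
|---|---|---|
| 0 | 0% | 80.0% |
| 0.1 | 0.5% | 80.4% |
| 0.2 | 2.1% | 81.6% |
| 0.3 | 4.8% | 83.6% |
| 0.4 | 9.1% | 86.4% |
| 0.5 | 15.5% | 89.9% |

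At r_own = 0.5, 865 × 0.75 ≈ 649 patients would give the same precision. With r_brain = 0.2 and r_own = 0.1 the sign reverses: √(0.96/0.99) = 0.985, so brain-volume adjustment has an SE 1.5% smaller.

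**6. Bias.** In 1,500 simulated trials per setting the treatment estimate stayed on its true value under either covariate. The largest deviation was 0.004, against an SE of about 0.07.

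**The case against.** The strongest answer is that the cross-reference was never meant to be applied word for word. For thalamus and cord it cannot be, since the outcome in 4.3.2 is brain volume. A reader who must substitute the outcome can equally substitute the baseline, because in 4.3.2 that covariate is the endpoint's own baseline and the sibling models follow the same practice. The sample code is also labelled draft. This stands for thalamus and cord: there the text leaves the covariate unspecified, and a reader should not infer that the SAP commits itself to the wrong one. It is weaker for black holes, where the authors did write a substitution and stopped at Y_ij.

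A second answer is that the gain may be nil. The thalamic and cord outcomes are percentage changes, already scaled to their own baseline. The black-hole endpoint is expressed as a radius, which is the natural scale if radius growth does not depend on lesion size; in that case own-baseline adjustment gained nothing. This also stands. It rules out quoting any single percentage as the loss, and rules out claiming as fact that baseline lesion volume determines how far Y can move.

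Third, the endpoints are exploratory and outside the testing hierarchy in SAP 2.1. That is correct and limits the consequence.

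**Conclusion.** The gap is real and small. SAP 4.4.3 names no baseline covariate for its three endpoints, and the only one it inherits belongs to a different structure. Read literally, this departs from the own-baseline practice of 4.3.2, 4.3.3, 4.4.2 and 4.4.4.

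A reader might infer that the dose effect would be biased or that a stated amount of power is lost. The documents support neither. Randomization keeps the estimate unbiased under either covariate, and the primary test, the hierarchy and type I error are untouched. The precision at stake for black holes ran from none to about 60% of the variance across the assumed growth laws in the first table, and higher in one favourable combination. For thalamus and cord it is about r squared, with r unknown, and can reverse slightly if whole-brain volume predicts better than own baseline. Priority: consider.

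**What to change.** In SAP 4.4.3 state that X_i contains the baseline of the structure analysed, together with the stratification factors:

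- thalamus: baseline thalamic volume;
- cord: baseline spinal cord volume;
- black holes: cube root of baseline total T1-hypo-intense lesion volume.

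Define Y_ij for thalamus and cord as percentage change in that structure, and say whether whole-brain volume stays as an additional covariate. Align the `Baseline` variable in the 4.3.2 sample code. An indicator for no lesion at baseline is optional in the black-hole model; its value depends on the same growth assumptions.

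The cost is a few lines of SAP text and one covariate per model. It needs no new data, visits or alpha. SAP 2.3 puts sponsor unblinding several weeks after the clinical cutoff. If that has already happened, record the choice as a dated clarification and report both adjustments.

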#### **4.4.4 Estimands for Proportion of Responders at Scheduled Visits**

**Estimand:** The estimand is the difference in the endpoint, as expressed by the odds ratio of being a responder, between the higher and approved dose of ocrelizumab arms in patients with RMS and regardless of adherence to the randomized treatment or use of an approved MS DMT medication.

##### **Endpoints:**

- Proportion of patients with no change in overall severity, improvement or worsening measured with patient global impression of severity at Week 48 and 120
- Proportion of patients with no change in overall MS symptoms, improvement or worsening measured with patient global impression of change at Week 48 and 120
- Proportion of patients with no change in upper limb function, improvement or worsening measured with patient global impression of change of upper limb function at Week 48 and 120

**Summary Measure and Primary Estimator:** Ordered logistic regression will be applied to the various responder definitions at each scheduled visit between the higher and approved dose of ocrelizumab arms. The fixed effects in the model will include independent variables of randomized treatment, baseline endpoint value, and the randomization stratification factors. The statistical significance of the estimated odds ratio will be calculated with the Wald test.

In order to estimate the estimand of interest, the same **intercurrent event** handling strategies as for primary estimand in Section 4.2.2 will be applied.

Only data up until Week 120 (inclusive) will be used in the analysis.

Missing data resulting from patients that withdraw their consent to participate in the study and/or a serious GCP breach will not be imputed (including following death).

#### **4.4.5 Estimands for Expected Counts at each Scheduled Visit**

**Estimand:** The estimand is the ratio of the mean endpoint between the higher and approved dose of ocrelizumab arms in patients with RMS and in the absence of treatment discontinuation and initiation of alternative MS treatments.

**Endpoints:**

- Total number of new or enlarging T2 lesions per MRI scan over the 120-week treatment period and at each scheduled visit
- Total number of T1Gd+ lesions over the 120-week treatment period and at each scheduled visit
- Total number of new T1-hypo-intense lesions (black holes) over the 120-week treatment period and at each scheduled visit

**Summary Measure and Primary Estimator:** Separate negative binomial models will be fitted to the data on the endpoints at each scheduled visit and for the total count over the 120-week treatment period. The mean function of the model will be parameterized using the log link function and the linear predictor will include as an offset either the log number of MRI scans for T1Gd+ lesions or log time in years of scan relative to baseline for new or enlarging T2 lesions and T1-hypo-intense lesions, an indicator variable for the assigned treatment and the randomization stratification factors as independent variables. The statistical significance of the estimated ratio of means will be calculated by using the Wald test.

In order to estimate the aforementioned estimand, the same **intercurrent event** handling strategies as those for brain volume in Section 4.3.2 will be applied.

Only data up until Week 120 (inclusive) will be used in the analysis.

Missing data resulting from patients that withdraw their consent to participate in the study and/or a serious GCP breach will not be imputed (including following death).

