4.5.7 MRI Sequences

MRI will be used to monitor CNS lesions in patients with MS and potentially other pathophysiology, such as inflammation and neurodegeneration. MRI scans of the brain,

and also of the upper part of the spine if technically possible will be obtained in all patients at study visits as indicated in [Appendix 1](#), [Appendix 2](#), and [Appendix 3](#).

The MRI sequences will be analyzed by a central reading facility ensuring the integrity and quality of the acquired data.

Qualifying MRI scans will be performed on healthy volunteers having provided informed consent at each MRI center as part of the scanner certification process with the MRI service provider, if not already available.

During the screening phase, one MRI scan will be performed, and it will serve as a baseline scan. Note that this baseline scan should be obtained at least 10 days prior to performing the baseline visit to allow time for the centralized reading center to assess its quality and for potential re-scans if needed.

Post-baseline, MRI scans will be obtained in all patients as per Schedule of Activities (SoA, see [Appendix 1](#), [Appendix 2](#), and [Appendix 3](#)). In addition, MRI scans will be obtained at *the* treatment discontinuation visit if one was not performed during the prior 4 weeks. MRI scans should occur within a window of ± 4 weeks of the scheduled visit, as per the schedules of activities (see [Appendix 1](#), [Appendix 2](#), and [Appendix 3](#)). During the OLE, MRI scans will be performed every 48 weeks (according to the yearly schedule as carried over from the double-blind treatment phase).

If patients receive corticosteroids for an MS relapse, every effort should be made to obtain scheduled MRI scan prior to the first corticosteroid dose. In patients receiving corticosteroids for an MS relapse, there should be an interval of 3 weeks between the last dose of corticosteroids and the MRI scan. For details of the MRI sequences, scanning acquisition sequences, methods, handling and transmission of the scans, certification of site MRI scanner, and the procedures for the blinded analysis of the scans at the central reading center, refer to the MRI Acquisition Procedures Manuals.

MRI assessments will include, but may not be limited to, T1-weighted scans before and after injection of Gd contrast, fluid-attenuated inversion recovery, proton density-weighted, and T2-weighted scans.

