## **4. STATISTICAL ANALYSES**

### **4.1 GENERAL CONSIDERATIONS**

All statistical hypotheses for the primary and secondary endpoints and treatment comparisons will be tested at the 5% significance level ( $\alpha=0.05$ ) against two-sided alternatives.

All primary and secondary efficacy endpoints will be stratified by region, age at screening, baseline EDSS and baseline body weight for analysis. The regional stratifications are United States and ROW. The age categories are  $\leq 45$  years and  $> 45$  years. The EDSS categories are  $< 4.0$  and  $\geq 4.0$ . The body weight categories are  $< 75$  kg and  $\geq 75$  kg.

The baseline for the primary endpoint is the date of randomization. The baseline value of the endpoint, e.g., EDSS, T25FWT and 9-HPT values, is the most recent value up to and including the date of randomization but before first infusion of study drug. A subject with delayed dosing may receive the first dose 2 weeks after the baseline visit; if an EDSS, T25FW or 9-HPT score is recorded between the randomization date and the date of the first dose, this value will be considered as a post-baseline assessment.

FAS will be used in the analysis of the primary and secondary estimands, and exploratory efficacy endpoints. Safety analysis set (SAS) will be used to summarize safety data. For analysis purposes, the time of treatment discontinuation will be defined as 24 weeks after the last dose prior to the date of treatment discontinuation recorded in the electronic Case Report Form (eCRF).

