#### Baseline MRI data:

- Number of gadolinium-enhancing T1 lesions at baseline (continuous and categorical analysis [0, 1, 2, 3,  $\geq 4$ ])
- Whole-brain volume at baseline
- T2 lesion volume at baseline
- Number of T2 lesions at baseline (continuous)

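### The exploratory MRI lesion-count models leave out the baseline lesion counts the trial collects, which costs some precision if those counts are prognostic but causes no bias

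*SAP*

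**What the plan says.** SAP 4.4.5 fits separate negative binomial models at each scheduled visit and for the total over 120 weeks. The log-link predictor has an offset, "either the log number of MRI scans for T1Gd+ lesions or log time in years of scan relative to baseline" for the other two lesion types, and then "an indicator variable for the assigned treatment and the randomization stratification factors as independent variables". SAP 4.1 names the stratification factors: "All primary and secondary efficacy endpoints will be stratified by region, age at screening, baseline EDSS and baseline body weight for analysis". None of them is an MRI variable.

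Baseline lesion data exist. Protocol 4.5.7 states: "During the screening phase, one MRI scan will be performed, and it will serve as a baseline scan". SAP 4.6.2 lists "Number of gadolinium-enhancing T1 lesions at baseline", and also the baseline number and volume of T2 lesions, but only for descriptive summaries. Protocol 6.4.4 treats T1Gd+ presence and T2 lesion count as subgroup factors, and SAP 4.2.4.1 keeps T1Gd+ presence for the primary estimand.

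Other models in the SAP do adjust for baseline:

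- **Brain volume (4.3.2):** the covariate term "is a vector containing the cube root of the baseline total brain volume and randomization stratification factors for patient". SAP 4.4.3 applies the same estimator to thalamic volume, spinal cord volume and T1-hypo-intense lesion radius.
- **NfL (4.3.3):** log baseline NfL.
- **EDSS change and patient-reported scores (4.4.2):** "baseline outcome, treatment-by-visit interaction, baseline outcome by visit interaction, along with the randomization stratification factors".
- **Ordinal global impressions (4.4.4):** the baseline endpoint value.

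The SAP gives no reason for treating the lesion counts differently, and 4.7 does not mention it.

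**The concern.** Lesion counts vary widely between patients. If patients with active lesions at screening form more lesions later, a model without that information pushes the difference into the dispersion parameter. The standard error of the log rate ratio then becomes larger than it need be. Both arms receive an active dose of the same drug, so any difference may be small and the width of the interval decides how informative the comparison is. The covariates that would help are already planned for the baseline tables, and these counts are the only MRI endpoints in the SAP modelled without a baseline MRI covariate. What is at stake is the precision of an exploratory comparison; no confirmatory conclusion depends on it.

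**Working it through.** **The plan's own figures.** The documents give no mean count, dispersion, precision or power for lesion counts, so there is no stated figure to reproduce for this point. The only planned calculation is for the primary endpoint, and it reproduces: (1.960 + 0.842)² / [(2/3)(1/3)(ln 0.66)²] = 7.85 / 0.0384 ≈ 205 events. It has no bearing on lesion counts.

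**Inputs from the documents.** 865 patients (SAP 2.2) randomized 2:1, so about 577 and 288. This is an upper bound on the patients contributing scans.

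**Assumed inputs.** A fraction p = 0.40 have T1Gd+ lesions at baseline, their later rate is r = 3 times that of the others, and the residual dispersion is k = 2. The mean μ ranges from 0.02 to 1 lesion per patient. For simplicity both arms have the same mean.

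**Formulas.** Var(log rate ratio) = V × (1/577 + 1/288), where the bracket is 0.005205.

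- Unadjusted: V = 1/μ + k_total, with k_total = (1 + k)(1 + CV²) − 1. CV² is the squared coefficient of variation of the patient means across the two baseline groups.
- Adjusted: V = 1 / E[μᵢ/(1 + kμᵢ)], averaged over the two baseline groups.

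**Worked case, μ = 1.**

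- Group means: 1/(0.6 + 0.4×3) = 0.556 without T1Gd+ lesions and 1.667 with them.
- CV² = 0.6×0.556² + 0.4×1.667² − 1 = 0.296.
- k_total = 3×1.296 − 1 = 2.889, so unadjusted V = 3.889.
- Adjusted: 0.6×0.556/2.111 + 0.4×1.667/4.333 = 0.3117, so V = 3.208.
- Variance reduction: 1 − 3.208/3.889 = 17.5%. The SE falls from 0.142 to 0.129, so the log-scale interval is about 9% narrower.

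| Mean lesions per patient | V unadjusted | V adjusted | Variance reduction | SE before → after |
|---|---|---|---|---|
| 1 | 3.889 | 3.208 | 17.5% | 0.142 → 0.129 |
| 0.3 | 6.222 | 5.714 | 8.2% | 0.180 → 0.172 |
| 0.1 | 12.889 | 12.500 | 3.0% | 0.259 → 0.255 |
| 0.05 | 22.889 | 22.542 | 1.5% | 0.345 → 0.343 |
| 0.02 | 52.889 | 52.571 | 0.6% | 0.525 → 0.523 |

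**Simulation.** With the same assumptions, mean 1 and a true rate ratio of 0.75, fitted models gave a variance reduction of 10 to 14%, below the formula's 17.5%. At mean 0.1 they gave about 2 to 4%. The average estimated rate ratio was 0.757 without the covariate and 0.754 with it, so neither model shows material bias.

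**If the assumptions move.** With p from 30 to 45%, r from 2 to 5 and k from 1 to 3, the formula gives variance reductions of 8 to 34% at mean 1, 3 to 19% at 0.3, and 0.2 to 7.5% across means of 0.02 to 0.1. A separate simulation used a standardized continuous baseline covariate with dispersion 2. It reduced the SE by 1.9 to 13.2% at mean 1 and by 0.1 to 2.7% at mean 0.05. When the covariate was not prognostic, the SE changed by no more than about 0.2% either way.

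**The case against.** Four points can be made against the concern.

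- **Consistency.** A reader might infer that the lesion-count models are the only efficacy models without baseline adjustment. The documents do not support that. The relapse-rate model in 4.4.6, the SAP's other count model, uses the same structure, and the Cox models for the primary and secondary endpoints are stratified by the randomization factors alone. The contrast holds only against the continuous, ordinal and volumetric models. This objection stands.
- **No baseline value of their own.** New or enlarging T2 lesions and new T1-hypo-intense lesions are counted from baseline onward, so only T1Gd+ has a true baseline counterpart. For the other two, baseline T1Gd+ and T2 counts are prognostic proxies. This also stands, but it does not remove a precision gain if the proxies predict later lesions.
- **Size.** If counts are very low in both arms, the gain nearly disappears, as the lower rows of the table show. No section states the expected counts, so neither a large nor a negligible gain can be claimed.
- **Fragility.** Per-visit models with few events already strain estimation. In simulations at mean 0.05 with four binary strata, only 172 to 183 of 200 runs per setting gave usable fits from both the current and the extended model. That is not due to the added covariate alone, but adding covariates without a fallback would be careless.

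**Conclusion.** The point holds as a minor efficiency gain. The three models in SAP 4.4.5 omit baseline lesion information that the trial has. If that information is prognostic, the rate ratios are less precise than they could be.

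Under the assumed values (40% with T1Gd+ lesions at baseline, rate ratio 3, dispersion 2), the variance reduction is roughly 10 to 17% at a mean of 1 lesion per patient. It is about 2 to 4% at 0.1 and about 1% (0.6 to 1.5%) at 0.02 to 0.05. In interval width these figures roughly halve. None of the assumed values comes from the documents.

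A reader might infer that the planned rate ratios are biased or invalid. They are not: under randomization, with a log link and a common treatment effect, adding a baseline main effect leaves the target rate ratio unchanged. Nor does the point touch the trial's conclusions, because SAP 4.4 classes these endpoints as exploratory and they are not in the testing hierarchy of SAP 2.1.

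**What to change.** In SAP 4.4.5:

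1. Add baseline T1Gd+ lesions (0 versus 1 or more) to all three models.
2. Add baseline T2 lesion count, on a log or cube-root scale fixed in advance, to the new or enlarging T2 and new T1-hypo-intense models.
3. State that a per-visit model that does not converge reverts to the current covariate set.
4. Give a simple rule for missing baseline lesion data that ignores treatment arm, so that patients are not dropped.

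Timing matters. SAP version 4 carries an approval stamp of 18 February 2025, the clinical cutoff was scheduled for December 2024, and database lock was to follow by several weeks. The documents do not show whether unblinding had already taken place. If it has, keep the planned model and report the adjusted one as a labelled supplementary analysis.

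The cost is a few SAP sentences and slightly more analysis work, with possible non-convergence at sparse visits that the fallback handles. No new data are needed.
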